## 6.2. Exclusion Criteria

Patients will be excluded from study enrollment if they meet any of the following criteria at screening and/or enrollment:

- [8] are investigative site personnel directly affiliated with this study and their immediate families. Immediate family is defined as a spouse, biological or legal guardian, child, or sibling.
- [9] are Lilly employees.
- [10] are currently enrolled in a clinical study involving an investigational product or any other type of medical research judged not to be scientifically or medically compatible with this study.
- [11] have participated, within the last 30 days, in a clinical study involving an investigational product. If the previous investigational product has a long half-life, 5 half-lives or 30 days (whichever is longer) should have passed.
- [12] have previously completed or withdrawn from this study or have previously received dulaglutide within the 3 months prior to Visit 1.
- [13] have known allergies to dulaglutide, or other GLP-1 receptor agonists.
- [14] have had any of the following cardiovascular conditions within the 3 months prior to Visit 1: acute myocardial infarction, New York Heart Association (NYHA) Class III or Class IV heart failure, or cerebrovascular accident (stroke).
- [15] have a known clinically significant gastric emptying abnormality or have undergone gastric bypass surgery or restrictive bariatric surgery.
- [16] have acute or chronic hepatitis, signs and symptoms of any other liver disease, or alanine aminotransferase (ALT) level >2.5 times the upper limit of the reference range, as determined by the local laboratory at Visit 1.
- [17] have a history of chronic pancreatitis or acute idiopathic pancreatitis, or were diagnosed with any type of acute pancreatitis within the 3 months prior to Visit 1.
- [18] have an estimated glomerular filtration rate (eGFR) <30 mL/min/1.73 m^2, calculated by the Japanese Society of Nephrology equation, at Visit 1 (eGFR [mL/min/1.73 m^2] = 194 × Cr-1.094 × Age-0.287 × 0.739 [if female]).
- [19] have any self or family history of type 2A or type 2B multiple endocrine neoplasia (MEN 2A or 2B) in the absence of known C-cell hyperplasia.

- [20] have any self or family history of medullary C-cell hyperplasia, focal hyperplasia, or carcinoma (including sporadic, familial, or part of MEN 2A or 2B syndrome).
- [21] have serum calcitonin  $\geq 20$  pg/mL, as determined by the local laboratory at Visit 1.
- [22] Positive human immunodeficiency virus (HIV) antigen and antibody, hepatitis C antibody, hepatitis B surface antigen, or syphilis at Visit 1.
- [23] have evidence of a significant, active uncontrolled endocrine or autoimmune abnormality, as judged by the investigator at Visit 1.
- [24] have a history of transplanted organ.
- [25] are receiving systemic glucocorticoid therapy.
- [26] have a history of active or untreated malignancy, or are in remission from a clinically significant malignancy during the 5 years prior to Visit 1.
- [27] have donated 400 mL or more blood in the last 12 weeks (males) or in the last 16 weeks (females), or any blood donation (including apheresis) within the last 4 weeks, or total volume of blood donation within 12 months is 1200 mL (males) / 800 mL (females) or more at Visit 1.
- [28] have an average weekly alcohol intake that exceeds 21 units per week (males up to age 65) and 14 units per week (females and males over 65) at Visit 1. (1 unit = 360 mL of beer; 150 mL of wine; 45 mL of distilled spirits.)
- [29] in the opinion of the investigator or sponsor, are unsuitable for inclusion in the study.

### **6.3. Lifestyle and/or Dietary Requirements**

Throughout the study, patients may undergo medical assessments and review of compliance with requirements before continuing in the study.

#### **6.3.1. Meals and Dietary Restrictions**

Study participants should be instructed to continue diet therapy during study period.

Solid Japanese standardized test meal (480 kcal, carbohydrate: protein: fat = 2.8:1:1) will be supplied for MTT. The menu will be prepared by managerial dietitian at study site. Identical meal will be supplied for each test. Patients should ingest standardized test meal within 15 minutes.

#### **6.3.2. Activity**

Study participants should be instructed to continue exercise therapy during study period.

### **6.3.3. *Blood Donation***

Study participants should be instructed not to donate blood or blood products during the study or for 4 weeks following the study.

### **6.4. *Screen Failures***

Individuals who do not meet the criteria for participation in this study (screen failure) may be re-screened once. The interval between re-screenings should be at least 2 weeks. Each time re-screening is performed, the individual must sign a new informed consent form (ICF) and will be assigned a new identification number.

## 7. Treatment

### 7.1. Treatment Administered

This study involves a comparison of dulaglutide 0.75 mg versus placebo administered once weekly as a subcutaneous injection by single-dose pen (SDP).

Investigational product will be injected subcutaneously in the abdomen. Trained site staff will administer the injection.

Table GBGK.2 shows the treatment regimens.

Treatment Name	Dulaglutide	Placebo
Dosage Formulation	single-dose pen	single-dose pen
Unit Dose Strength(s)/ Dosage Level(s)	0.75 mg (0.5 mL)	0 mg (0.5 mL)
Route of Administration	subcutaneous injection	subcutaneous injection
Dosing Instructions	once weekly	once weekly

The investigator or his/her designee is responsible for maintaining accurate records of investigational product dispensing and collection.

#### 7.1.1. Packaging and Labeling

The sponsor will provide dulaglutide and placebo in SDPs. Each SDP (0.75 mg dulaglutide in 0.5 mL OR placebo in 0.5 mL) is packaged in cartons of 4 pens.

The investigational product will be labeled according to the country's regulatory requirements.

### 7.2. Method of Treatment Assignment

Patients who meet all criteria for enrollment will be randomized at Visit 3 in a 1:1 ratio to dulaglutide 0.75 mg or placebo. Assignment to treatment groups will be determined by a randomization table.

#### 7.2.1. Selection and Timing of Doses

Investigational product will be administered once weekly. It is recommended that patients receive the investigational product on the same day each week. The doses will be administered at approximately the same times on each day.

The actual time of all dose administrations will be recorded in the patient's case report form (CRF).

### 7.3. Blinding

Single-blind (patient-blind) is adopted for this study. Glucose data (including CGM data) will not be disclosed to patients during study period.

Blinding will be maintained throughout the conduct of the study as described in the separate Blinding Plan.

### 7.4. Dose Modification

Dose adjustments are not allowed in this study.

### 7.5. Special Treatment Considerations

#### 7.5.1. *Management of Increased Hypoglycemia Risk*

If a hypoglycemic event occurs, the patient should record in the study diary the episode and associated symptoms and/or signs, and rescue treatment (if taken).

Study site personnel will record information related to hypoglycemia such as start and end date and time of the episode, hypoglycemia signs and symptoms present. Following definitions and criteria will be used for categorizing an episode considered to be related to hypoglycemia (the PG values in this section refer to values determined by a laboratory or International Federation of Clinical Chemistry and Laboratory Medicine plasma-equivalent glucose meters and strips) (American Diabetes Association 2005):

- **Documented symptomatic hypoglycemia** is defined as any time a patient feels that he/she is experiencing symptoms and/or signs associated with hypoglycemia, and has a PG level of  $\leq 70$  mg/dL ( $\leq 3.9$  mmol/L).
- **Asymptomatic hypoglycemia** is defined as an event not accompanied by typical symptoms of hypoglycemia but with a measured PG of  $\leq 70$  mg/dL ( $\leq 3.9$  mmol/L).
- **Probable symptomatic hypoglycemia** is defined as an event during which symptoms of hypoglycemia are not accompanied by a PG determination (but that was presumably caused by a PG concentration of  $\leq 70$  mg/dL [ $\leq 3.9$  mmol/L]).
- **Severe hypoglycemia** is defined as an episode requiring the assistance of another person to actively administer carbohydrate, glucagon, or other resuscitative actions. These episodes may be associated with sufficient neuroglycopenia to induce seizure or coma. Plasma glucose measurements may not be available during such an event, but neurological recovery attributable to the restoration of PG to normal is considered sufficient evidence that the event was induced by a low PG concentration.
- **Nocturnal hypoglycemia** is defined as any hypoglycemic event that occurs between bedtime and waking.

If a hypoglycemic event meets the criteria of severe, it needs to be recorded as serious on the adverse event (AE) CRF and reported to Lilly as a serious adverse event (SAE).

### **7.5.2. Management of Severe Hyperglycemia**

If a patient experiences severe hyperglycemia, the patient must discontinue from the study. Severe hyperglycemia is defined as follows: the patient's fasting blood glucose concentrations are >270 mg/dL (>15.0 mmol/L) on two or more occasions.

### **7.6. Preparation/Handling/Storage/Accountability**

The investigator or designee must confirm appropriate temperature conditions have been maintained, as communicated by sponsor, during transit for all investigational product received and any discrepancies are reported and resolved before use of the study treatment.

Only participants enrolled in the study may receive investigational product or study materials, and only authorized site staff may supply or administer investigational product. All investigational product should be stored in an environmentally controlled and monitored (manual or automated) area in accordance with the labeled storage conditions with access limited to the investigator and authorized site staff.

The investigator, institution, or the head of the medical institution (where applicable) is responsible for study treatment accountability, reconciliation, and record maintenance (such as receipt, reconciliation, and final disposition records).

### **7.7. Treatment Compliance**

The investigational product will be administered at the clinical site, and documentation of treatment administration will occur at the site.

### **7.8. Concomitant Therapy**

Concomitant non-study antidiabetic medication is not allowed in this study. Concomitant systemic glucocorticoid therapy is also not allowed in this study.

Patients on stable concomitant medication other than antidiabetic medication or systemic glucocorticoid therapy at the time of study entry should continue their regular, unchanged dose throughout the study.

In general, additional concomitant medication should be avoided; however, rescue medicine such as acetaminophen (up to 2 g) may be administered at the discretion of the investigator for treatment of headaches etc. Any medication used during the course of the study must be documented.

### **7.9. Treatment after the End of the Study**

Not applicable.

## 8. Discontinuation Criteria

Patients discontinuing from the study prematurely for any reason should complete AE and other follow-up procedures per Section 2 of this protocol.

### 8.1. Discontinuation from Study Treatment

Discontinuation of the investigational product for abnormal liver tests **should be considered** by the investigator when a patient meets 1 of the following conditions after consultation with the Lilly designated medical monitor:

- ALT (alanine aminotransferase) or AST (aspartate aminotransferase)  $>8\times$  ULN (upper limit of normal)
- ALT or AST  $>5\times$  ULN sustained for more than 2 weeks or
- ALT or AST  $>3\times$  ULN and total bilirubin level (TBL)  $>2\times$  ULN or International Normalized Ratio (INR)  $>1.5$  or
- ALT or AST  $>3\times$  ULN the appearance of fatigue, nausea, vomiting, right upper-quadrant pain or tenderness, fever, rash, and/or eosinophilia ( $>5\%$ )
- ALP (alkaline phosphatase)  $>3\times$  ULN
- ALP  $>2.5\times$  ULN and TBL  $>2\times$  ULN
- ALP  $>2.5\times$  ULN with the appearance of fatigue, nausea, vomiting, right quadrant pain or tenderness, fever, rash, and/or eosinophilia ( $>5\%$ ).

In addition, patients will be discontinued from the investigational product in the following circumstances:

- For inadvertently enrolled patients for whom it was determined that continued treatment with investigational product would not be medically appropriate (see Section 8.1.1);
- The patient's fasting blood glucose concentrations are  $>270$  mg/dL ( $>15.0$  mmol/L) on two or more occasions (see Section 7.5.2);
- The patient becomes pregnant during the study, in which case, the patient must discontinue the study immediately and Lilly or its designee is to be informed immediately;
- The patient is diagnosed with acute pancreatitis or acute hepatitis (see Section 9.2.2.1);
- The patient develops Exclusion Criterion [18] (eGFR  $<30$  mg/min/1.73m^2);
- The patient is diagnosed with C-cell hyperplasia or medullary thyroid carcinoma;
- The patient uses or needs to use additional antidiabetic medication or prohibited medication (systemic glucocorticoids).

#### 8.1.1. Discontinuation of Inadvertently Enrolled Patients

If the sponsor or investigator identifies a patient who did not meet enrollment criteria and was inadvertently enrolled, a discussion must occur between the Lilly clinical pharmacologist and the

investigator to determine if the patient may continue in the study. If both agree it is medically appropriate to continue, the investigator must obtain documented approval from the Lilly clinical pharmacologist to allow the inadvertently enrolled patient to continue in the study with or without continued treatment with investigational product.

## 8.2. Discontinuation from the Study

Patients will be discontinued in the following circumstances:

- Enrollment in any other clinical study involving an investigational product or enrollment in any other type of medical research judged not to be scientifically or medically compatible with this study
- Participation in the study needs to be stopped for medical, safety, regulatory, or other reasons consistent with applicable laws, regulations, and good clinical practice (GCP)
- Investigator Decision
  - the investigator decides that the patient should be discontinued from the study
  - if the patient, for any reason, requires treatment with another therapeutic agent that has been demonstrated to be effective for treatment of the study indication, discontinuation from the study occurs prior to introduction of the new agent
- Patient Decision
  - the patient, or legal representative, requests to be withdrawn from the study.

## 8.3. Patients Lost to Follow-up

A patient will be considered lost to follow-up if he or she repeatedly fails to return for scheduled visits and is unable to be contacted by the study site. Site personnel are expected to make diligent attempts to contact patients who fail to return for a scheduled visit or were otherwise unable to be followed up by the site.

## 9. Study Assessments and Procedures

Section 2 lists the Schedule of Activities, detailing the study procedures and their timing.

Appendix 2 lists the laboratory tests that will be performed for this study.

Appendix 5 provides a summary of the maximum number and volume of invasive samples, for all sampling, during the study.

Appendix 6 provides a summary of MTT procedures.

Unless otherwise stated in subsections below, all samples collected for specified laboratory tests will be destroyed within 60 days of receipt of confirmed test results. Certain samples may be retained for a longer period, if necessary, to comply with applicable laws, regulations, or laboratory certification standards.

### 9.1. Efficacy Assessments

This section is not applicable for this study.

### 9.2. Adverse Events

Investigators are responsible for monitoring the safety of patients who have entered this study and for alerting Lilly or its designee to any event that seems unusual, even if this event may be considered an unanticipated benefit to the patient.

The investigator is responsible for the appropriate medical care of patients during the study.

Investigators must document their review of each laboratory safety report.

The investigator remains responsible for following, through an appropriate health care option, AEs that are serious or otherwise medically important, considered related to the investigational product or the study, or that caused the patient to discontinue the investigational product before completing the study. The patient should be followed until the event resolves, stabilizes with appropriate diagnostic evaluation, or is reasonably explained. The frequency of follow-up evaluations of the AE is left to the discretion of the investigator.

After the ICF is signed, study site personnel will record, via CRF, the occurrence and nature of each patient's preexisting conditions, including clinically significant signs and symptoms of the disease under treatment in the study. Additionally, site personnel will record any change in the condition(s) and the occurrence and nature of any AEs.

The investigator will interpret and document whether or not an AE has a reasonable possibility of being related to study treatment, study device, or a study procedure, taking into account the disease, concomitant treatment or pathologies.

A "reasonable possibility" means that there is a potential cause and effect relationship between the investigational product, study device, and/or study procedure and the AE.

Planned surgeries should not be reported as AEs unless the underlying medical condition has worsened during the course of the study.

If a patient's investigational product is discontinued as a result of an AE, study site personnel must report this to Lilly or its designee via CRF.

### **9.2.1. Serious Adverse Events**

An SAE is any AE from this study that results in one of the following:

- death
- initial or prolonged inpatient hospitalization
- a life-threatening experience (that is, immediate risk of dying)
- persistent or significant disability/incapacity
- congenital anomaly/birth defect
- important medical events that may not be immediately life-threatening or result in death or hospitalization but may jeopardize the patient or may require intervention to prevent one of the other outcomes listed in the definition above
- when a condition related to the investigational device (SDP) necessitates medical or surgical intervention to preclude either permanent impairment of a body function or permanent damage to a body structure, the serious outcome of "required intervention" will be assigned.

Study site personnel must alert the Lilly clinical research physician (CRP)/clinical pharmacologist, or its designee, of any SAE as soon as practically possible.

Additionally, study site personnel must alert Lilly Global Patient Safety, or its designee, of any SAE within 24 hours of investigator awareness of the event via a sponsor-approved method. If alerts are issued via telephone, they are to be immediately followed with official notification on study-specific SAE forms. This 24-hour notification requirement refers to the initial SAE information and all follow-up SAE information.

Although all AEs are recorded in the CRF after signing informed consent, SAE reporting to the sponsor begins after the patient has signed informed consent and has received investigational product. However, if an SAE occurs after signing informed consent, but prior to receiving investigational product, AND is considered reasonably possibly related to a study procedure then it MUST be reported.

Investigators are not obligated to actively seek AEs or SAEs in patients once they have discontinued from and/or completed the study (the patient summary CRF has been completed). However, if the investigator learns of any SAE, including a death, at any time after a patient has been discharged from the study, and he/she considers the event reasonably possibly related to the study treatment or study participation, the investigator must promptly notify Lilly.

Pregnancy (maternal or paternal exposure to investigational product) does not meet the definition of an AE. However, to fulfill regulatory requirements any pregnancy should be reported following the SAE process to collect data on the outcome for both mother and fetus.

### 9.2.1.1. Suspected Unexpected Serious Adverse Reactions

Suspected unexpected serious adverse reactions (SUSARs) are serious events that are not listed in the investigator's brochure and that the investigator reports as related to investigational product or procedure. Lilly has procedures that will be followed for the recording and expedited reporting of SUSARs that are consistent with global regulations and the associated detailed guidances.

### 9.2.2. Adverse Events of Interest

#### 9.2.2.1. Pancreatitis

Acute pancreatitis is defined as an AE of interest in all trials with dulaglutide, including this trial. Acute pancreatitis is an acute inflammatory process of the pancreas that may also involve peripancreatic tissues and/or remote organ systems (Banks and Freeman 2006). The diagnosis of acute pancreatitis requires 2 of the following 3 features:

1. Abdominal pain, characteristic of acute pancreatitis (generally located in the epigastrium and radiates to the back in approximately half the cases [Banks and Freeman 2006, Koizumi et al. 2006]; the pain is often associated with nausea and vomiting);
2. Serum amylase (total and/or pancreatic) and/or lipase  $\geq 3 \times$  ULN; or
3. Characteristic findings of acute pancreatitis on computed tomography (CT) scan or magnetic resonance imaging (MRI).

If acute pancreatitis is suspected, appropriate laboratory tests (including levels of amylase [total and pancreatic] and lipase) should be obtained via the local laboratory. Imaging studies, such as abdominal CT scan with or without contrast, MRI, or gallbladder ultrasound, should be performed. If laboratory values and/or abdominal imaging support the diagnosis of acute pancreatitis, the patient must discontinue therapy with investigational product and will also be discontinued from the study. The most appropriate diabetes therapeutic regimen will be decided by the investigator, based on the patient's clinical status. A review of the patient's concomitant medications should be conducted to assess any potential causal relationship with pancreatitis.

Each case of AE of pancreatitis must be reported. If typical signs and/or symptoms of pancreatitis are present and confirmed by laboratory values (lipase or amylase) and imaging studies, the event must be reported as an SAE. For a potential case that does not meet all of these criteria, it is up to the investigator to determine the seriousness of the case (AE or SAE) and the relatedness of the event to investigational product.

In addition to the diagnostic assessment in patients who develop symptoms of acute pancreatitis, each patient will have measurements of total amylase and lipase at Visit 3, 7, 9, 13, and early termination visit to assess any potential effects of dulaglutide on the exocrine pancreas (refer to the Schedule of Activities, Section 2). Further diagnostic assessment per Lilly algorithm for assessment of asymptomatic pancreatic hyperenzymemia will be required whenever lipase and/or total amylase are  $\geq 3 \times$  ULN at any time during the study. If this situation occurs at Visit 13, the

patient will undergo this additional work, and the data will be collected in the clinical trial database.

#### **9.2.2.2. C-Cell Hyperplasia and C-Cell Neoplasms**

Individuals with personal or family history of certain thyroid or nonthyroid endocrine abnormalities or certain preexisting laboratory and genetic characteristics will be excluded from the study (see Section 6.2). The assessment of thyroid safety during the trial will include reporting of thyroid TEAEs and measurements of calcitonin according to the Study Schedule (Section 2) at Visit 3, 7, 9, 13, and ET visit. The purpose of calcitonin measurements is to assess the potential of dulaglutide versus placebo to affect the thyroid C-cell function, which may indicate development of C-cell hyperplasia and neoplasms.

Patients who develop serum calcitonin increases  $\geq 50\%$  of the mean of the baseline and screening values AND an absolute value  $\geq 20$  pg/mL and  $< 35$  pg/mL at Visit 13 will be asked to repeat the measurement within 1 month. If this repeat value is increasing ( $\geq 10\%$  increase), the patient will be recommended that he or she undergo additional endocrine assessment and longer-term follow-up by an endocrinologist to exclude a serious adverse effect on the gland.

Patients with an increase in serum calcitonin  $\geq 50\%$  of the mean of the baseline and screening values AND an absolute value  $\geq 35$  pg/mL at Visit 13 will be recommended to immediately undergo additional endocrine assessments and longer-term follow-up by an endocrinologist.

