## 5. Study Design

### 5.1. Overall Design

Study GBGK is a Phase 4, single-center, randomized, cross-over, single-blind, placebo-controlled study to evaluate glucodynamic effects of dulaglutide after standardized test meal in Japanese patients with T2D.

The study includes a 10- to 28-day screening period, a 4-week treatment period (Period 1), a 4- to 6-week washout period, and a 4-week treatment period (Period 2).

[figure not shown]
Screening tests will be performed at Visit 1. After confirming eligibility, the patient will be randomized in a 1:1 ratio to dulaglutide 0.75 mg or placebo treatment in Period 1.

Meal tolerance test will be performed at baseline, 1, 2, and 4 weeks for each period. Time points for blood sampling will be 0, 30, 60, 90, 120, 180, and 240 minutes after the start of standardized test meal. Satiety will be also assessed at 0, 60, 120, 180, and 240 minutes after the start of standardized test meal. Detailed schedule of MTT is described in [Appendix 6](#). After completion of Period 1, all patients must have a 4- to 6-week washout period, and then will start Period 2 on the opposite treatment (patients taking dulaglutide will be switched to placebo and patients taking placebo will be switched to dulaglutide).

This is a single-blind study, and the treatment assignments will be blinded to patients until study completion.

Study governance considerations are described in detail in [Appendix 3](#).

[Figure GBGK.5.1](#) illustrates the study design.

▲ Meal tolerance test (240 minutes at 0, 1, 2, 4 weeks)

Abbreviations: CGM = continuous glucose monitoring; dula = dulaglutide; n = number of patients.

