## Appendix 6. Meal Tolerance Test

Time	Procedure
-120 min	Physical exam, vital signs (sitting) Weight (only Day 1, Day 29, Day 57, and Day 85) ECG (only Day 1 and Day 57) Urine sampling for pregnancy test (only Day 1 and Day 57, if needed) Urinalysis and UACR (only Day 1, Day 29, Day 57, and Day 85) Blood sampling for hematology, clinical chemistry, endocrinology, HbA1c (only Day 1, Day 29, Day 57, and Day 85) Blood sampling for glucose, insulin, c-peptide, glucagon, and triglyceride (for 0 min) Satiety evaluation (VAS) (for 0 min)
0 min	Start standardized test meal a
30 min	Blood sampling for glucose, insulin, c-peptide, glucagon, and triglyceride
60 min	Blood sampling for glucose, insulin, c-peptide, glucagon, and triglyceride Satiety evaluation (VAS)
90 min	Blood sampling for glucose, insulin, c-peptide, glucagon, and triglyceride
120 min	Blood sampling for glucose, insulin, c-peptide, glucagon, and triglyceride Satiety evaluation (VAS)
180 min	Blood sampling for glucose, insulin, c-peptide, glucagon, and triglyceride Satiety evaluation (VAS)
240 min	Blood sampling for glucose, insulin, c-peptide, glucagon, and triglyceride Satiety evaluation (VAS)
After MTT	Dose of dulaglutide 0.75 mg or placebo (except Days 29 and 85)

Abbreviations: HbA1c = glycated hemoglobin; min = minutes; MTT = meal tolerance test; UACR = urine albumin/creatinine ratio; VAS = visual analog scale.

a Japanese standard test meal (480 kcal, carbohydrate: protein: fat = 2.8:1:1) should be ingested within 15 min.

---

**Appendix 7. Protocol Amendment H9X-JE-GBGK(a)  
Summary: A Phase 4 Study to Evaluate Glucodynamic  
Effects of Dulaglutide in Japanese Patients with Type 2  
Diabetes Mellitus**

---

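### Both calcitonin action tiers are tied to Visit 13, so a qualifying rise at Visit 7, Visit 9 or early termination has no calcitonin-specific repeat or referral

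*Protocol*

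**What the plan says.** Protocol Section 9.2.2.2 calls for "measurements of calcitonin according to the Study Schedule (Section 2) at Visit 3, 7, 9, 13, and ET visit". Its stated purpose is to compare dulaglutide with placebo for effects on thyroid C-cell function. Two action tiers follow. Both require a rise of at least 50% over the mean of the baseline and screening values.

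- **Lower tier, 20 to <35 pg/mL:** the patient "at Visit 13 will be asked to repeat the measurement within 1 month". Endocrine referral is recommended if the repeat is up by 10% or more.
- **Upper tier, ≥35 pg/mL:** patients at or above this value in "pg/mL at Visit 13 will be recommended to immediately undergo additional endocrine assessments", with longer-term specialist follow-up.

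No tier is written for Visit 7, Visit 9 or ET. Elsewhere calcitonin appears as exclusion criterion [21] (≥20 pg/mL at Visit 1) and in the laboratory list of Appendix 2. Section 8.1 stops treatment on a diagnosis of C-cell hyperplasia or medullary thyroid carcinoma, not on a calcitonin value. SAP Section 9.4.3 only lists and flags endocrinology results.

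**The concern.** A trigger at the last visit can work in a parallel-group trial, where every patient's final visit ends the assigned treatment. Here the patients change over: "patients taking dulaglutide will be switched to placebo and patients taking placebo will be switched to dulaglutide". For the dulaglutide-first sequence the rule therefore reads the end-of-placebo sample and passes over the end-of-dulaglutide sample. Followed to the letter, such a patient with ≥35 pg/mL at Visit 7 gets no calcitonin-specific referral unless the value is still raised at Visit 13, weeks after exposure ended. A patient who withdraws has a scheduled ET sample but no tier to apply to it, and no later scheduled sample.

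The placebo-first sequence has a smaller version of the problem. A value of 20 pg/mL or more would have excluded the patient at Visit 1. The same value at Visit 7, before that patient's first dulaglutide dose at Visit 9, prompts no stated step. What is at stake is patient follow-up, not the efficacy inference.

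**Working it through.** The plan gives no figure to reproduce on this point. The check is a comparison of the provisions plus day arithmetic. Days are nominal and ignore the ±1-day visit allowance.

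**Inputs**
- Visit days from the Schedule of Activities: Visit 3 = Day 1, Visit 7 = Day 29, Visit 9 = Day 57, Visit 13 = Day 85. The washout allowance is +14 days.
- Calcitonin belongs to the endocrinology panel (Appendix 2). Appendix 6 schedules "Blood sampling for hematology, clinical chemistry, endocrinology, HbA1c (only Day 1, Day 29, Day 57, and Day 85").
- Injections are given on Days 1, 8, 15 and 22 of a period (Schedule of Activities). Appendix 6 confirms that none is given at the end of a period: "Dose of dulaglutide 0.75 mg or placebo (except Days 29 and 85"). The last Period 1 dose is therefore on Day 22.
- 12 patients are randomized 1:1 and one dropout is assumed (Section 10.1).

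**Which samples the rule covers**

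| Sample | Day | Dulaglutide-first | Placebo-first | Tier applies |
|---|---|---|---|---|
| Visit 7 | 29 | end of dulaglutide | end of placebo | no |
| Visit 9 | 57 to 71 | before placebo | before dulaglutide | no |
| Visit 13 | 85 to 99 | end of placebo | end of dulaglutide | yes |
| ET | varies | whichever period is under way | whichever period is under way | no |

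**Delays for a dulaglutide-first patient**
- Visit 7 to Visit 13: 85 − 29 = 56 days; with the longest washout, 56 + 14 = 70.
- Last dulaglutide dose to Visit 13: 85 − 22 = 63 days; 63 + 14 = 77.
- Visit 7 to Visit 9: 57 − 29 = 28 days; 28 + 14 = 42. Visit 9 falls within one month of Visit 7 on the nominal schedule, but not if most of the washout allowance is used.

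**Counts**
- Dulaglutide-first patients: 12 ÷ 2 = 6.
- End-of-period values if all 12 complete: 12 × 2 = 24. Visit 13 supplies 12 (6 after dulaglutide, 6 after placebo). Visit 7 supplies the other 12 (6 and 6), and none of these is covered.
- ET: about one patient, on the protocol's own dropout assumption.

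**Neighbouring rules**
- The amylase and lipase rule in Section 9.2.2.1 uses the same visits, yet requires further work-up for a threshold value "at any time during the study". It then adds what to do when the finding arises at Visit 13.
- The hepatic rule in Section 9.4.5.1 names no visit.
- Of these laboratory rules, only the calcitonin rule is confined to the last visit.

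**The case against.** The strongest reply is that other safeguards exist.

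- **General oversight.** Section 9.2 says "Investigators must document their review of each laboratory safety report", and Section 9.4.5 has the sponsor review laboratory analytes periodically. A footnote in Appendix 5 already allows extra safety samples for this panel, so a repeat after Visit 7 or ET is permitted. This stands as mitigation. None of these provisions sets a calcitonin threshold, requires a repeat or directs a referral.
- **The patient is still on study at Visit 7.** Calcitonin is measured again at Visits 9 and 13, so an explicit exit rule matters most at Visit 13. A persistent rise would still be caught there. That is a fair reading of the intent. It does not cover ET, gives no criterion for the Visit 9 value, and delays the upper tier, whose action is meant to be immediate.
- **Low likelihood.** Criteria [19] to [21] screen out the patients at highest risk, and exposure is four doses of the approved dose. Nothing in the documents shows that any of the 12 would reach a tier. This is accepted, and no expected harm is claimed.
- **Size of the gap.** About 6 of the 12 uncovered Visit 7 values follow placebo. The directly relevant set is the other 6 or so, plus about one ET patient. This is also correct.
- **Early terminators.** Section 9.2.1 relieves sites of actively seeking adverse events after discontinuation, but the ET report is still reviewed and medically important events are still followed. So an ET result would be seen, although no stated calcitonin rule would follow from it.

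**Conclusion.** The concern holds. As written, the calcitonin rule omits the end-of-dulaglutide sample for about 6 of 12 patients and can never apply to a patient who terminates early. For the dulaglutide-first sequence, the first value that can trigger a tier comes 56 to 70 days after Visit 7 and 63 to 77 days after the last dulaglutide dose. This is a stated safety rule that misses the relevant sample when followed, not merely a missing detail. It should be corrected.

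The conclusion assumes an even split between sequences, nominal visit days and the planned 12 patients. It is limited to calcitonin-specific action, since general review and adverse event follow-up remain. The gap depends on period and not on treatment, so it does not affect the dulaglutide-versus-placebo comparison. A secondary ambiguity is that the baseline in the reference mean is not tied to a visit. Visit 3 is the natural reading, but the SAP uses a Day 1 baseline for each period for pharmacodynamic and vital sign data, and calcitonin is also drawn at Visit 9.

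**What to change.** In both tiers of Protocol Section 9.2.2.2, replace the reference to Visit 13 with any post-baseline measurement. This covers Visits 7, 9, 13 and ET and matches the scope of the enzyme rule. It is better than listing Visits 7, 13 and ET, which would leave Visit 9 without a rule.

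Allow the Visit 9 sample to serve as the lower-tier repeat for Visit 7 when it falls within one month, and otherwise take an unscheduled repeat. State that the baseline in the reference mean is Visit 3. The thresholds and the content of the referral stay as they are, for the sponsor's medical staff to confirm.

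The cost is one or two sentences in a protocol amendment and no added scheduled sample. The downside is an occasional unscheduled repeat or referral in a patient who already meets the sponsor's own threshold.
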